9.4.5 ANALYSIS OF SECONDARY SAFETY ENDPOINTS

The Safety population will be the analysis population for all safety analyses.

Secondary Endpoint (5) Comparison of incidence of adverse events.

Data collection: Adverse Events will be tabulated for both the test and reference groups. All AEs and SAEs will be MedDRA-coded and summarized by treatment arm. In addition, the number and proportion of AEs and SAEs will be calculated for each group. For each MedDRA-coded medical term, the proportion of subjects who experience at least one of the following will be reported and compared.

Adverse event

- Adverse event related to treatment
- Serious adverse event
- Serious adverse event related to treatment
- Adverse event leading to study discontinuation
- Serious adverse event leading to study discontinuation

Classification of AEs will also be presented and compared. Events will be reported by MedDRA system organ class and preferred term. Adverse Events will be compared by severity and device relatedness between the test and reference groups.

Acceptance Criteria: There is no defined endpoint acceptance criteria for the comparison of adverse events.

Statistical Analysis Method: A two-sided Fisher's Exact Test will compare (test versus reference) rate of incidence of adverse events by six months post-operative. Assessment of this is independent of the primary study endpoints.

Secondary Endpoint (6) Comparison (test to reference group) of non-increase in subject dyspareunia scores from baseline to 6-months post-operative.

Data collection: Individual subject dyspareunia will be assessed using the relevant sexual discomfort module of the validated Female Sexual Function Index (FSFI). Higher scores indicate good sexual function with little or no sexual discomfort, and lower scores indicate poor sexual function with higher levels of sexual discomfort. Scores of zero indicate no sexual activity and will not be included in comparison of non-increase in dyspareunia.

Acceptance Criteria: A subject level failure is defined as a decrease in sexual function score (signifying an increase in dyspareunia). Endpoint success is defined as the same or lower rate of FSFI score decrease in the test group at six months when compared to the reference group at six months.

Statistical Analysis Method: Comparison (test versus reference group) of failure rates from baseline to six-month follow-up will be made using a two-sided Fisher's Exact Test. Assessment of this is independent of the primary study endpoints.

Secondary Endpoint (7) Comparison (test to reference group) of non-increase in subject pain scores from baseline to 6-months post-operative.

Data collection: Individual subject pain will assed using a validated 11-point numerical pain rating scale, where "0" corresponds to no pain and "10" corresponds to the most pain possible. Pain score will be collected at all study timepoints and unexpected visits; however, statistical assessment will be performed between baseline and six-month score.

Acceptance Criteria: A subject level failure is defined as an increase in reported subject pain score. Endpoint success is defined as the same or lower rate of increase in reported pain in the test group at six months when compared to the reference group at six months.

Statistical Analysis Method: Comparison (test versus reference group) of failure rates from baseline to six-month follow-up will be made using a two-sided Fisher's Exact Test. Assessment of this is independent of the primary study endpoints.

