- (4) Relationship of implant passing events to adverse events. The frequency of implant passing following cuff closure associated with an Adverse Event will be evaluated through six-weeks post-operative.
- (5) Comparison of incidence of adverse events. Adverse events and serious adverse events will be tabulated for both the test and reference groups.
- (6) Comparison of change in dyspareunia. Non-increase in reported individual subject dyspareunia from baseline to 6-month follow-up will be compared (test versus reference group) using the relevant sexual discomfort module of the Female Sexual Function Index (FSFI).
- (7) Comparison of change in pain. Non-increase in reported individual subject pain from baseline to 6-month follow-up will be compared (test versus reference group) using an 11-point Numerical Rating Scale.

Study Population:

Women above the age of 18 who are undergoing laparoscopic hysterectomy and meet all of the inclusion criteria and none of the exclusion criteria will be eligible for this study.

Sample Size

For the purposes of assessing safety and effectiveness, a target of 59 women will be enrolled in a ratio of 2:1 test to reference (39 test and 20 reference subjects). This is based on a goal of 35 test subjects and an expected 10% of patients lost to follow-up.

Prescreening and informed consent will take place prior to surgery. Enrollment will take place during surgery once it has been confirmed that no intra-operative exclusion criteria are met. Subjects who meet one or more intra-operative exclusion criteria will not be enrolled but will receive standard hysterectomy procedure and follow-up care as they otherwise would.

Inclusion Criteria

- 1. Provision of signed and dated Informed Consent Form
- 2. Stated willingness to comply with all study procedures, including participation in follow-up visits and telephonic follow-up
- 3. Female 18 years or older
- 4. Indicated for Laparoscopic Hysterectomy (may include TLH, LAVH, robotic assisted vaginal hysterectomy)

Exclusion Criteria

Pre-operative Exclusion Criteria

- 1. History of HIV
- 2. History of Hepatitis C

- 3. History of diabetes, that in the opinion of the investigator may delay healing
- 4. Current use of systemic corticosteroids
- 5. Active infection of genitals, vagina, cervix, uterus or urinary tract
- 6. Active bacteremia, sepsis or other active systemic infection
- 7. Presence of Sextually Transmitted Infection (STI)

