12-months long. Consequently, this study is expected to take a total of 15 to 17 months from beginning of enrollment to completion of follow-up. Additionally, study blinding will be removed after the last subject completes their six-week follow-up timepoint, and 6 and 12-month follow-up will be collected unblinded. Data will be submitted for regulatory

study follow-up after 6 and 12 months.

Participant Duration: Intervention will occur at the time of surgery and subjects will complete a

12-month follow-up program, including in-person visits at one week, six weeks, and six months, as well as a telephone follow-up at 12-months.

review following unblinding at six weeks, and again after completion of

Statistical Methods: Analysis Populations:

Intent-to-treat population (ITT): This population will include all subjects enrolled and randomized to test or reference treatment. Subjects will be analyzed according to the treatment to which they were randomized,

regardless of the treatment they actually received.

Safety population: This population will include all subjects enrolled and randomized to test or reference treatment. Subjects will be analyzed according to the treatment that they received; patients randomized to the reference arm that receive Zip-stitch™ will be included in the Zip-stitch™ safety population. Similarly, patients randomized to the Zip-stitch™ arm that receive sutures will be included in the reference safety population.

Primary and secondary efficacy endpoint analyses will be performed on the ITT population. All safety analyses will be performed on the Safety population.

Efficacy Analysis:

Unless otherwise stated the analyses of efficacy endpoints will be based on the ITT population as follows.

One-sided endpoint analyses will be performed with 80% statistical power; corresponding *p*-values will be reported, and all two-sided analyses and comparisons between groups will be performed assuming a 0.05 significance level. The corresponding *p*-values and 95% confidence intervals (CIs) will be reported.

Primary Efficacy Endpoint:

Frequency of spontaneous implant passing events will be reported through six weeks. Event frequency will be numerically compared to a performance target of 5%.

Secondary Efficacy Endpoints:

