Frequency of implant passing incidents found to be associated with an Adverse Event will be reported. Failure in this endpoint is defined, on a per patient basis, as the presence of a spontaneous implant passing event (one or more clips being passed) determined by a blinded study investigator to be associated with an Adverse Event (AE), where "Associated" is defined as a device-related AE that is temporally related to the implant passing event. See Section 9.4.2 for a detailed description of investigator determination of Adverse Event relatedness to implant passing events.

Frequency of implant passing (either clips or sutures) will be explicitly collected at each followup visit; however, events may be reported between visits or during unexpected visits. When implant passing is reported, subjects will be asked to collect and provide passed implants, and an in-person evaluation will be performed, involving a visual cuff closure and healing assessment.

(5) Comparison of Incidence of adverse events

The number of adverse events and serious adverse events, as well as the proportion of subjects with adverse events, will be summarized by treatment arm, severity, and relatedness to device. Adverse events will be coded using the validated MedDRA system. By-subject listings will be provided for all safety data. Incidence of adverse events will then be compared using Fisher's

Exact test to assess possible significance or relationship of cuff closure device to adverse event rate.

(6) Comparison of change in dyspareunia

Dyspareunia will be pre-operatively baselined and assessed at each follow-up timepoint, including any unexpected visits, using the sexual pain and discomfort domain (four questions) from the validated Female Sexual Function Index (FSFI).^{21,22} Individual success is defined as non-increase in dyspareunia from baseline to six months. Fisher's Exact Test will be used to compare this measure between test and reference groups.

(7) Comparison of change in pain

Patient pain will be pre-operatively baselined and assessed at each follow-up timepoint, including any unexpected visits, using a validated 11-point numerical rating scale²³ (no pain: 0 – the most pain: 10). Individual success is defined as non-increase in pain between baseline and six months. Fisher's Exact Test will be used to compare this measure between test and reference groups.

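### Zero FSFI scores are dropped whatever the timepoint or reason, so a woman who stops sexual activity because of pain leaves the six-month dyspareunia comparison

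*Combined protocol and SAP*

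**What the plan says.** Section 3.2 (6) scores the sexual pain domain of the FSFI at baseline and at each follow-up. It sets the subject-level rule: "Individual success is defined as non-increase in dyspareunia from baseline to six months". It does not mention zero scores.

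Section 9.4.5 (6) explains that higher scores mean less discomfort, and defines failure for a woman as any fall in her score. It then adds: "Scores of zero indicate no sexual activity and will not be included in comparison of non-increase in dyspareunia". At group level, "Endpoint success is defined as the same or lower rate of FSFI score decrease in the test group at six months", judged against the reference group. The formal test follows: "Comparison (test versus reference group) of failure rates from baseline to six-month follow-up will be made using a two-sided Fisher's Exact Test". The Synopsis (1.1) sets the level: "all two-sided analyses and comparisons between groups will be performed assuming a 0.05 significance level".

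Section 9.4.10 allows imputation for this endpoint only when a woman is lost to follow-up after her six-week visit. Its sensitivity analyses concern the primary endpoint.

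**The concern.** A fall from a positive baseline score to zero is arithmetically a decrease, and so a failure under the plan's own definition. The zero-score exclusion removes the woman before that definition can be applied. If she stopped because intercourse hurt, the endpoint loses one of the outcomes it most needs to count, from both numerator and denominator. If this happens more often with clips than with suture, the test arm looks better than it is.

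The documents make the possibility real without establishing it. Section 2.3.2 lists a theorised contribution of the clips to dyspareunia while they degrade. Section 4.2 puts degradation at 5 to 8 months, so the six-month assessment falls inside that period. The abstinence required by Section 5.3 is a minimum of six weeks and does not by itself explain a zero at six months.

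Section 3 says that data through six months may support market clearance. The Synopsis and Section 6.3 have the data unblinded after the last six-week visit (Section 8.1 places unblinding after the six-month visits). Both are reasons to fix the handling of zeros in advance.

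**Working it through.** **Numbers expected at six months.** The plan gives no sample size, event rate or inactivity rate for this endpoint, so the starting point is the enrolment target, which reproduces:

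- Test: 35 / 0.9 = 38.9, rounded up to 39.
- Reference: 39 / 2 = 19.5, rounded up to 20.
- Total: 39 + 20 = 59, as stated in the Synopsis.
- After 10% loss: 39 × 0.9 = 35.1 and 20 × 0.9 = 18, so about 35 test and 18 reference women, before any are dropped for zero scores.

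**What happens to each pattern of scores under the written rule**

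| Baseline | Six months | Handling as written |
|---|---|---|
| Positive | Positive, same or higher | Success |
| Positive | Positive, lower | Failure |
| Zero | Any | Excluded (reasonable: no interpretable change) |
| Positive | Zero | Excluded, although the score fell |

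The last row is the problem. The Section 9.4.10 rules do not reach it, because a woman who attends and scores zero is not lost to follow-up.

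**Illustration 1 (all counts assumed).** Among women active at both times, 5 of 25 test and 3 of 15 reference women worsen. Further women go from positive to zero, and counting them adds each to both numerator and denominator.

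| Positive-to-zero, test / reference | Test | Reference | Success rule | Fisher p |
|---|---|---|---|---|
| Excluded as written | 5/25 = 20.0% | 3/15 = 20.0% | Met | 1.00 |
| 1 / 0 counted | 6/26 = 23.1% | 3/15 = 20.0% | Not met | 1.00 |
| 4 / 0 counted | 9/29 = 31.0% | 3/15 = 20.0% | Not met | 0.50 |
| 4 / 2 counted | 9/29 = 31.0% | 5/17 = 29.4% | Not met, by 1.6 points | 1.00 |
| 4 / 3 counted | 9/29 = 31.0% | 6/18 = 33.3% | Met | 1.00 |

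**Illustration 2 (all counts assumed).** Illustration 1 starts from a tie, so any small change can tip it. This one starts from an advantage for the test arm. Take 80% active at baseline, giving 28 test and 14 reference women, with 2 ordinary worsenings in each arm. Let s test women and no reference women fall to zero. The written rule gives 2/(28 − s); counting them gives (2 + s)/28; the reference rate is 2/14 = 14.3%.

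| s | As written | Counted as failures | Success as written / counted |
|---|---|---|---|
| 0 | 2/28 = 7.1% | 2/28 = 7.1% | Met / met |
| 2 | 2/26 = 7.7% | 4/28 = 14.3% | Met / met |
| 3 | 2/25 = 8.0% | 5/28 = 17.9% | Met / not met |
| 6 | 2/22 = 9.1% | 8/28 = 28.6% | Met / not met |

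Three such women reverse the result here; none, one or two do not. Fisher p-values stay above 0.05 throughout. Other runs, with 60%, 80% and 100% active at baseline and about 10% ordinary worsening, also gave p above 0.05. In those runs success was already not met under the written rule, so counting the zeros changed the rates but not the conclusion.

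**The case against.** The strongest counter-argument is about size. The documents give no rate of inactivity, no causes and no direction by arm, so pain as the reason is a hypothesis. Putting every new zero in the test arm is one-sided: inactivity close to the 2:1 allocation leaves almost no gap (31.0% against 29.4%), and one more reference zero reverses the direction. The planned Fisher test gives p = 0.50 even in the four-to-none case. All of this stands, and it limits what can be said about magnitude.

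The women are also not lost to the trial. Their scores appear in the individual listings (9.4.9), and general pain is compared at six months under endpoint (7). Dyspareunia reported as an adverse event would be tabulated, and Section 3.3 notes any association of visible implant material with dyspareunia. The number and percentage reporting in Section 9.4.1 would show a reduced denominator by arm. These are indirect, however. General pain is not dyspareunia, and a reduced denominator does not separate baseline zeros from new ones.

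Finally, secondary endpoints are labelled exploratory in the Synopsis and unpowered in Section 9.2, and Section 4.2 acknowledges the limits of using a single FSFI domain. That justifies a low grade. It does not justify a rule that removes a possible failure from its own endpoint.

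**Conclusion.** The concern holds as a minor one. As written, the rule excludes baseline-active women who score zero at six months, which is selection on a post-randomisation state that the outcome can cause. No dedicated by-arm count and no sensitivity analysis covers them.

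Because success rests on a numerical same-or-lower comparison in small arms, one to three such women in the test arm alone were enough to change the result in the two worked illustrations. Those counts are assumed. The true size and direction of bias cannot be derived from the documents, could be nil if inactivity is balanced, and would be very unlikely to show in the Fisher test. Primary endpoints are unaffected.

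**What to change.** Keep the stated analysis and state explicitly that it excludes zeros at either timepoint. Before unblinding, add:

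1. A table by arm that separates women scoring zero at baseline from women with a positive baseline who score zero at six months.
2. A sensitivity analysis of endpoint (6) counting every positive-to-zero change as a failure, reported beside the main result with the same success rule and Fisher test.

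The cost is one table and one extra analysis from scores already collected, with no new visits, instruments or subjects. The drawback is that the sensitivity analysis will count some women in both arms who are inactive for unrelated reasons, so it gives a bound and not an explanation. If the sponsor wants to separate the two groups, one case report form item on the reason for inactivity would do it. That is optional and goes beyond the minimum change.

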9.4.6 BASELINE DESCRIPTIVE STATISTICS

Demographic characteristics (age, ethnicity), height and weight, and disease characteristics will be summarized using descriptive statistics. Subjects in the ITT and Safety populations will be summarized within each treatment group and overall.

9.4.7 PLANNED INTERIM ANALYSES

There is no interim analysis planned. Primary endpoint analysis and reporting will take place after completion of all six-week follow-up. This report will be considered the final study report and will completely assess the primary study endpoint. There will be additional supplementary reports with follow-up endpoint analysis at 6 and 12-months. See study design rationale for additional details.

9.4.8 SUB-GROUP ANALYSES

There are no subgroup-analyses planned.

9.4.9 TABULATION OF INDIVIDUAL PARTICIPANT DATA

Individual participant data will be listed by measure and time point.

9.4.10 MISSING DATA & DATA IMPUTATION

Because implant passing is expected to be spontaneous, missing data will not be imputed for analysis of the primary study endpoint. Instead, if a subject is lost to follow-up prior to their six-week in-person visit, they will be included in the ITT population, but any incomplete data collection will be excluded from the total population evaluated for the primary study endpoint. For example, completed one-week follow-up data from a subject lost to follow-up between their one and six week visits will be included, but the uncompleted six-week data will be excluded, and they will not be included in the efficacy endpoint population totals for uncompleted follow-up timepoints. Data may be imputed based on existing data averages for subjects lost to follow-up after their six-week visit as part of additional study analysis, such as the 12-month unblinded follow-up reporting.

Sensitivity analysis will be performed on ITT population evaluation of the primary endpoint where all missing data are imputed as successes and separately as failures. Results of these analyses will be presented alongside primary endpoint evaluation. Every effort will be made to minimize missing data.

Additionally, any cases of vaginal cuff closure performed with a rescue method in accordance with protocol Section 6.5.1 will have their primary endpoint value set to missing. Their values will be imputed using multiple imputation. Additional information will be provided in the statistical analysis plan (SAP). These cases will also be included in sensitivity analysis determining possible effect of exclusion of these subjects from primary endpoint analysis.

Data imputation may be performed for appropriate secondary endpoints. Imputation will only be performed for secondary endpoints evaluating, or based on evaluation of, a status (as opposed to an incidence) and if a subject is lost to follow-up *after* their six-week visit. Data for subjects lost to follow-up before their six-week visit will not be imputed. Secondary endpoints that may allow for data imputation include (1) status of cuff closure, (2) status of cuff healing, (6) change in dyspareunia, and (7) change in pain.

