Due to the nature of implant passing, the data imputation strategy for the analysis of the primary study efficacy endpoint will exclude from analysis any incomplete follow-up from subjects lost to follow-up prior to their six-week follow-up visit. For example, one-week follow-up data from a subject lost to follow-up between one and six weeks will be included, but the uncompleted six-week data will be excluded, and they will not be included in the efficacy endpoint population totals for uncompleted follow-up timepoints. However, as detailed in the data imputation section of this protocol (Section 9.4.10), sensitivity analysis will be performed on primary endpoint evaluation where all missing data are imputed as successes and separately as failures. Every effort will be made to minimize missing data.

As implant passing is expected to be a spontaneous event with a low occurrence rate (<10%), any method of assumed incidence prior to six weeks is not practical. Instead, exclusion of lost subjects from both the numerator and denominator of implant passing analysis prevents biased subject exclusion and misrepresentative increases in endpoint population size. Furthermore, subjects who experience an implant passing event are more likely to report such an experience than subjects who experience no such event and therefore exclusion of lost subjects from the population total provides the strictest imputation strategy for this endpoint. After completion of six-week follow-up, implant passing data may be imputed for unblinded supplementary reporting based on average existing implant passing data. However, as the primary study endpoints conclude after six weeks, this imputation will be for supplemental analysis only. After six months clips have sufficiently degraded and are therefore unlikely to pass, and even less likely to be identified as having passed by a patient.

It is not expected that the primary study safety endpoint will be subject to reporting bias. As a significant clinical event, vaginal cuff dehiscence is unlikely to not be reported or to be subject to recall bias.

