9.3 POPULATIONS FOR ANALYSES

Intent-to-treat population (ITT): This population will include all subjects enrolled and randomized to test or reference treatment. Subjects will be analyzed according to the treatment to which they were randomized, regardless of the treatment they actually received.

Safety Population: This population will include all subjects enrolled and randomized to test or reference treatment. Subjects will be analyzed according to the treatment that they received; patients randomized to the reference arm that receive Zip-stitch™ will be included in the Zip-stitch™ safety population. Similarly, patients randomized to the Zip-stitch™ arm that receive sutures will be included in the reference safety population.

Primary and secondary efficacy analyses will be performed on the ITT population. All safety analyses will be performed on the Safety population.

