Secondary Endpoint (3) Comparison of implant passing rates.

Data collection: Implant passing rates will be calculated and the percentage of subjects experiencing one or more implant passing events will be compared between the test and control groups at six weeks and at six months.

Acceptance Criteria: Endpoint success is defined as a percentage of subjects experiencing implant passing in the test group less than or equal to that of the reference group.

Statistical Analysis Method: A two-sided Fisher's Exact Test will compare (test versus reference) percentage of subjects experiencing implant passing events between test and reference groups. Assessment of this is independent of the primary study endpoints.

Secondary Endpoint (4) Relationship of Implant passing to Adverse Events.

Data collection: Frequency of implant passing events associated with an Adverse Event will be evaluated through six-weeks post-operative. Associating implant passing to an Adverse Event will include consideration of temporal and possible causal relationship. The AE relatedness terms described in Section 8.3.3 will be utilized in determination of implant passing to a given Adverse Event, where "relatedness to study intervention" is replaced with "relatedness to implant passage." This will not replace determination of relatedness to the study device, which will be performed separately according to study safety reporting details. Adverse Events determined to be 'probably' or 'definitely' related to an implant passing event will be considered a per patient failure of the primary efficacy endpoint. Relationship of implant passing events to AEs will be reported independently and compared between test and control groups.

Acceptance Criteria: Endpoint success is defined as a percentage of subjects experiencing implant passing event related to an AE in the test group less than or equal to that of the reference group.

Statistical Analysis Method: A two-sided Fisher's Exact Test will compare (test versus reference) percentage of subjects experiencing implant passing event associated with an AE between test and reference groups. Assessment of this is independent of the primary study endpoints.

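### Section 9.4.10 discards the observed six-week implant-passing outcome of women closed by a rescue method and imputes it, against the ITT rule and the plan to compare an observed rate with 5%.

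*Combined protocol and SAP*

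**What the plan says.** - **Rescue rule (9.4.10).** Any case closed by a rescue method under 6.5.1 "will have their primary endpoint value set to missing. Their values will be imputed using multiple imputation". Details are deferred to the SAP, and no imputation model is given in the text.
- **No imputation otherwise (9.4.10, opening).** For the same endpoint, "missing data will not be imputed for analysis of the primary study endpoint". Women lost before six weeks leave the evaluated total instead. Section 4.2, writing about lost women, gives the reason: "any method of assumed incidence prior to six weeks is not practical".
- **Analysis population (9.3).** Primary efficacy is analysed by ITT, in the randomised arm, "regardless of the treatment they actually received".
- **Endpoint and target (3.1, 4.1, 9.1).** A woman fails if she has one or more spontaneous passing events, of clips or sutures. The aim is to observe a failure rate below 5%, compared numerically without a test. Section 9.1 words the target in terms of patients who have clips applied.
- **Rescue cases (6.5.1).** They are protocol deviations, but are included in the primary efficacy analysis and in the ITT and safety populations.
- **Sensitivity analyses (9.4.10).** All missing values are counted as successes and, separately, as failures. A further analysis looks at excluding rescue cases.
- **Secondary Endpoint (3) (9.4.4).** The percentage of women with passing "will be compared between the test and control groups at six weeks and at six months".

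**The concern.** Setting a value to missing matters only where a value exists. Rescued women stay in follow-up and are asked about passing at each visit, so the rule will normally remove a recorded outcome. The plan then treats the two groups the wrong way round: women whose outcome is truly unknown are not imputed, while women whose outcome is known are.

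The woman keeps her place in the ITT denominator, but her result is set aside because of the treatment she received. The rate set against 5% is then partly modelled, whereas Section 4.1 says it is the observed rate. At this sample size the margin is a single woman.

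**Working it through.** **Inputs from the documents.** Goal of 35 evaluable test women with 10% loss (4.1); 30 to 40 requested for the test group (9.2); target below 5% (3.1).

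**Assumptions.** The documents give no rescue rate. The only evidence is 10 of 10 closures achieved with the device (2.2); zero rescues in 10 has an exact 95% interval of 0% to 30.8% (upper limit 1 − 0.025^(1/10)). Imputation is taken to have no covariates, with many imputations.

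**Plan's own figures.** 35/0.9 = 38.9, rounded up to 39 test; 39/2 = 19.5, rounded up to 20 reference; total 59. These reproduce.

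**Events allowed.** The largest k with k/n < 0.05 is 1 for every n from 30 to 40. For example, 1/35 = 2.86% and 2/35 = 5.71%, while 2/40 = 5.00% is not below 5%.

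**Effect of the rule.** Let x be all observed passers, r the rescued women and e the passers among them. The observed rate is x/n. Under the rule the pooled rate tends to (x − e)/(n − r). With a prior weight a on each outcome (a near 0, 0.5 or 1), the example with x − e = 1 becomes (1 + r(1 + a)/(35 − r + 2a))/35.

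Example: n = 35, x = 2, e = 1.

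| | r = 1 | r = 2 |
|---|---|---|
| Observed, as randomised | 2/35 = 5.71% (missed) | 2/35 = 5.71% (missed) |
| As written, a near 0 | 1/34 = 2.94% (met) | 1/33 = 3.03% (met) |
| As written, a = 0.5; 1 | 2.98%; 3.02% (met) | 3.11%; 3.18% (met) |
| Rescue cases excluded | 1/34 = 2.94% | 1/33 = 3.03% |
| All missing = success, nobody lost | 1/35 = 2.86% | 1/35 = 2.86% |
| All missing = failure, nobody lost | 2/35 = 5.71% | 3/35 = 8.57% |
| All missing = failure, 4 of 39 lost | (1+1+4)/39 = 15.4% | (1+2+4)/39 = 17.9% |

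**Direction.** If the observed result meets the target, there is at most one passer, so the rule gives at most 1/(n − r). For n = 30 to 40 and r = 1 to 3 this is at most 1/27 = 3.7%. Under these assumptions the verdict can move from missed to met, but not the other way.

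**When rescued women pass nothing (e = 0).** The rule raises the rate slightly. With x = 1 and r = 3, observed is 1/35 = 2.86% and as written is 1/32 = 3.12%. The verdict is the same.

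**Illustrative probabilities.** Take n = 35 and 3% passing among women not rescued (assumed). The excess chance of meeting the target as written, over using observed outcomes, from exact binomial sums:

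| Passing after rescue | r = 1 | r = 2 | r = 3 |
|---|---|---|---|
| 0% | 0 | 0 | 0 |
| 3% | 1.1 points | 2.2 points | 3.4 points |
| 10% | 3.7 points | 7.5 points | 11.2 points |

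With no rescues the excess is 0. The 10% row is an upper illustration: Section 4.2 expects passing below 10% in general and says nothing about passing after rescue.

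**The case against.** The best defence is that the rule aims at a different quantity. Section 9.1 frames the target around patients with clips applied. A woman randomised to clips but closed with suture may carry no clip, so her outcome says little about clips. Imputing what would have happened without rescue is a recognised hypothetical strategy. This has force, but the documents never state that aim, and 9.3 and 4.1 state the opposite one.

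It is also fair that the opening no-imputation sentence is explained through loss to follow-up, and that the rescue paragraph begins with the word *Additionally*. A reader might infer a flat contradiction inside 9.4.10. The text does not force that, because the rescue rule can be read as an exception. Likewise 6.5.1 only requires that these women be included, and an imputed woman still is. The firm conflicts are with 9.3 and 4.1.

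A reader might infer that a rescued woman's passing event disappears from the report. It does not. Secondary Endpoint (3) gives the six-week rate by arm in ITT, imputation is confined to status endpoints "as opposed to an incidence", and individual data are listed (9.4.9). What remains is two six-week rates for one arm, with the imputed one as primary.

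A reader might also see a further conflict in Secondary Endpoint (4), which calls passing linked to an adverse event a primary failure. It adds nothing here, since any passing event is already a failure under 3.1.

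Finally, the all-success and all-failure analyses do bracket the observed result. With one rescue, a passer, and nobody lost, the all-failure figure equals it. With more rescues or any losses it does not, and no planned analysis of the primary endpoint is stated to use the observed values.

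**Conclusion.** The point holds and should be fixed. As written, 9.4.10 replaces observed outcomes by imputed ones in a primary analysis that 9.3 and 4.1 describe as ITT and observed. That conflict needs no numerical assumption.

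The size is conditional. One overwritten event can turn 5.7% (missed) into about 2.9% to 3.2% (met) with 35 women and one or two rescues, given imputation without covariates. It would be too strong to infer that the rule will change the result or that it always favours the device. The only clinical evidence is 10 of 10 closures, so there may be no rescues. With none, or with no passer among them, the verdict stands, and in the latter case the rule slightly raises the rate.

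**What to change.** In 9.4.10, replace the set-to-missing rule with wording such as: *Subjects closed by a rescue method are analysed in their randomised arm using the observed implant-passing outcome through six weeks; where it was not observed, the loss-to-follow-up rule applies. Multiple imputation of these subjects is a sensitivity analysis, alongside the planned exclusion, all-success and all-failure analyses.*

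Reconcile 9.1 with this by saying whether the target refers to all women randomised to the device or to those with clips applied. If a rate without rescue is wanted, state it as a supplementary aim.

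The cost is two sentences in 9.4.10 and one in 9.1, with no new data. There are two downsides. The primary rate may be less favourable if a rescued woman passes an implant. It may also be slightly diluted if rescued women carry no clip and pass nothing (2.86% against 3.12% with one passer and three rescues of 35); the exclusion analysis shows that effect. The change concerns the analysis only, not the surgical rescue.
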